### **6.1. Subjects randomized to NO-maintenance therapy: the WATCH group**

The subjects randomized to no-treatment will be followed up very closely:

Subjects will have study visits every 4 weeks for the first four months and then every 6 weeks for a total of 24 months of follow-up from randomization. The first visit after randomization will be Visit 1. Visit 1 will be scheduled as soon as possible after randomization.

Subjects will be called by phone by a study coordinator, nurse or physician between each clinic visit for a review of their clinical history to detect any symptoms or signs suggestive of relapse of vasculitis. Should the patient report a symptom or sign suggestive of relapse, she/he will be seen in clinic within the following week for full evaluation. The phone call will be done about 14 days after the clinic visit for the first four months and about 3 weeks after the clinic visit once the subject is followed every 6 weeks. The phone call will be done within a +/- 5 days window. Subject will be trained on the symptoms to watch for and instructed to call study team if such a symptom occurs, without waiting for study phone call or study visit.

Study visits will take place either in the UNC Kidney and Hypertension Clinic, at the Clinical and Translational Research center (CTR) or in the UNC Hospitals Infusion Clinic. Subjects will be examined by a nephrologist, either their regular nephrologist or a nephrologist who is a member of the study team. Study-specific procedures for each visit are outlined below.

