**Schedule of Visits and Events: WATCH group (no-maintenance therapy)**

Visit	Physical Exam & Vitals	BVAS †	CDA ‡	Concomitant Meds	QOL Q'naire	Adverse Events	Blood Collection for Research	Urine pregnancy test	Lab Data Collection
Enrollment	X	X		X	X		X	X	X
SOC visits until B Cell recovery	optional	optional		X				optional	X
Visit 1 (week 0)	X	X	X	X	X	X	X	X	X
14 days post-monthly visit call		Script		X					
Visit 2 (week 4)	X	X		X		X		X	X
Visit 3 (week 8)	X	X		X		X		X	X
Visit 4 (week 12)	X	X		X		X	X	X	X
Visit 5 (week 16)	X	X		X		X		X	X
Visit 6 (week 22)	X	X		X	X	X	X	X	X
Visit 7 (week 28)	X	X		X		X		X	X
Visit 8 (week 34)	X	X		X		X	X	X	X
Visit 9 (week 40)	X	X		X		X		X	X
Visit 10 (week 46)	X	X		X	X	X	X	X	X
Visit 11 (week 52)	X	X	X	X		X		X	X
Visit 12 (week 58)	X	X		X		X	X	X	X
Visit 13 (week 64)	X	X		X		X		X	X
Visit 14 (week 70)	X	X		X	X	X	X	X	X
Visit 15 (week 76)	X	X		X		X		X	X
Visit 16 (week 82)	X	X		X		X	X	X	X
Visit 17 (week 88)	X	X		X		X		X	X
Visit 18 (week 94)	X	X		X	X	X	X	X	X
Visit 19 (week 100)	X	X		X		X		X	X
Visit 20 (week 106)	X	X	X	X		X	X	X	X

†

BVAS = Birmingham Vasculitis Assessment Score

‡

CDA = Combined Damage Assessment Index

Xo

Schedule of Visits and Events: TREATMENT GROUP

Visit	Physical Exam & Vitals	BVAS †	CDA ‡	Concomitant Meds	QOL Q'naire	Adverse Events	Blood Collection for Research	Urine pregnancy test	Lab Data Collection	Maintenance Therapy with Rituximab*
Enrollment	X	X		X	X		X 	X	X	
SOC until B Cell recovery	optional	optional		X				optional	X	
Visit 1/ (week 0)	X	X	X	X	X	X	X*	X	X	X*
Visit 2 (8 to 12 wks after V1)	X	X		X		X		X	X	
Visit 3 (8 to 12 wks after V2)	X	X		X	Xi	X		X	X	X*
Visit 4 (8 to 12 wks after V3)	X	X		X		X		X	X	
Visit 5 (8 to 12 wks after V4)	X	X		X	Xi	X	X*	X	X	X*
Visit 6 (8 to 12 wks after V5)	X	X		X		X		X	X	
Visit 7 (8 to 12 wks after V6)	X	X		X	Xi	X	X*	X	X	X*
Visit 8 (8 to 12 wks after V7)	X	X		X		X		X	X	
Visit 9 (8 to 12 wks after V8)*	X	X		X	Xi	X	X*	X	X	X*
Visit 10 (8 to 12 wks after V9)*	X	X		X		X		X	X	
Visit 11 (8 to 12 wks after V10)*	X	X	X	X		X		X	X	
Visit 12 (8 to 12 wks after V11)*	X	X		X		X		X	X	
Visit 13 (8 to 12 wks after V12)*	X	X		X		X		X	X	

† BVAS = Birmingham Vasculitis Assessment Score

‡ CDA = Combined Damage Assessment Index

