## APPENDIX C: Script for patient scheduled monitoring calls

Days 15, 30, 45, etc.

"Hello,

This call is to check on how you are feeling and assess whether your vasculitis remains inactive

I will ask you a few questions about symptoms you may feel that could suggest the vasculitis is active or that you may have an infection. In answering, please think about the period of time since your last visit with Dr xxx. If you have any of these symptoms, please also tell me if this is new (in the last 2 weeks, or older) and how severe it is (mild, moderate or severe)"

- 1- Fever
- 2- Ear pain or change in hearing
- 3- Red or painful eyes
- 4- Bleeding from the nose, or sinus pain
- 5- Hoarseness, "air hunger", difficulty taking a deep breath
- 6- Cough or shortness of breath
  - a. If cough, does anything come out? What color? Any blood in the sputum?
  - b. If shortness of breath: is it with exertion (with walking, doing house chores or going up stairs for example), or even at rest? Is it worse at night? Do you feel that you get short of breath more easily than before?
- 7- Chest pain.
  - a. How often, is it on exertion or even at rest? How long does it last? Does it change with position?
- 8- Any nausea or vomiting? How many times did you vomit? Was there any blood in it? When was the last time you vomited? Are you able to eat and keep your food down?
- 9- Any abdominal (belly) pain or diarrhea? Constipation?
  - a. If diarrhea: are the stool soft, black and smelly? Is there any blood in the stool?
- 10- Any joint pain? Are the painful joints red, hot or swollen? How long do they last?
- 11- Any rash? If yes, where is it? Is it on both sides of the body or only one side?
  - a. Is it painful?
  - b. Any open sores
- 12- Any unusual headaches? Is it severe (cannot function)? Is it unusual for you?
- 13- Any new numbness, tingling or weakness in any limb (arms, legs, fingers, toes)?

14- Is there anything else you are concerned about that I did not ask you about?

If any of the above are answered positively:

“Have you called your doctor or the study doctor about this?”

- If yes: “what did the doctor tell you it was?
  - Did she/he prescribe any new medication? Any other change in medication?
  - Do you feel better since?”
- If no: I will relay this to the study doctor and he/she will get back with you and/or see you in clinic in the next 2-3 days.

If none of the questions are answered positively:

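### The WATCH group's between-visit call script has no direct question on urine changes, urinary symptoms or leg or face swelling, and its 'If yes' branch should be aligned with section 6.1

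*Combined protocol and SAP*

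**What the plan says.** Section 6.1 sets up the calls for the WATCH group: "Subjects will be called by phone by a study coordinator, nurse or physician between each clinic visit". Their purpose is to review the history for anything that might point to relapse. They fall about 14 days after the visit in the first four months and about 3 weeks after it once visits are 6 weeks apart, within 5 days either way. In the WATCH schedule of visits, the row labelled "14 days post-monthly visit call" carries the entry 'Script' in the BVAS column (as the table was extracted), so the script is the relapse check planned for the call.

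Appendix C gives the script. It says that it looks for symptoms of active vasculitis or of infection. Thirteen specific items follow, then an open one: "Is there anything else you are concerned about that I did not ask you about". After any positive answer the caller asks: "Have you called your doctor or the study doctor about this". If the patient has, the caller asks what the doctor thought it was, then "Did she/he prescribe any new medication? Any other change in medication", then whether the patient feels better, and the branch ends. If the patient has not, the script reads: "If no: I will relay this to the study doctor and he/she will get back with you and/or see you in clinic", with 2-3 days given as the time.

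Outside the script, section 6.1 states a rule without exceptions: "Should the patient report a symptom or sign suggestive of relapse, she/he will be seen in clinic within the following week for full evaluation". It also provides for training: "Subject will be trained on the symptoms to watch for and instructed to call study team if such a symptom occurs".

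**The concern.** The script is silent on the organ that matters most in this population. The Introduction says that glomerulonephritis occurs in most patients and lists renal-limited disease as one of four phenotypes. Section 4.1 admits patients with biopsy-proven pauci-immune crescentic glomerulonephritis, and section 4.3 recruits from a kidney clinic. Section 8.4 names glomerulonephritis among its examples of major relapse. Section 7.2 names the urinary tract as an infection site, so the gap also touches the script's second stated aim.

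These patients are off maintenance immunosuppression by randomization, and the call is the planned check between visits. A patient whose disease was renal only would go through all 13 items without being asked about urine or swelling. What is at stake is a delay in evaluating a renal relapse that has produced a symptom the patient could have reported if asked.

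The second, smaller matter is that the branching question pools the patient's own doctor with the study doctor. A patient who called only an outside doctor falls into the 'If yes' branch, which has no relay. The caller may be a coordinator, so the script itself does not then bring the symptom to a study physician.

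**Working it through.** **Item check.** The 13 specific items of Appendix C cover: fever; ear or hearing; eyes; nose or sinus; hoarseness or air hunger; cough or breathlessness; chest pain; nausea or vomiting; abdominal pain or bowel changes; joints; rash; headache; numbness, tingling or weakness.

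- Items on urine color, blood, foam or volume, on urinary symptoms, or on leg or face swelling: 0 of 13. Swelling appears only in item 10, for painful joints.
- Section 8.4 gives three examples of major relapse. Alveolar hemorrhage has a matching prompt (blood in sputum, item 6). Mononeuritis with motor deficits has one (limb weakness, item 13). Glomerulonephritis has none.

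**Branch check.** A relay to the study doctor is written in 1 of 2 branches ('If no' only).

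**Number of calls.** The WATCH schedule has visits at weeks 0, 4, 8, 12 and 16, then every 6 weeks to week 106. That is 5 + (106 - 16)/6 = 5 + 15 = 20 visits, hence 4 + 15 = 19 intervals and at most 19 between-visit calls.

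**Wait from call to next visit.** Inputs: call timing and its 5-day window from section 6.1, and the visit window of one week from section 6.3.1. The script's own header lists days 15, 30, 45 and so on; I use section 6.1, which ties the calls to the visits. The preceding visit is taken as on schedule.

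- 4-week phase: nominal 28 - 14 = 14 days. Range 14 - 7 - 5 = 2 to 14 + 7 + 5 = 26 days.
- 6-week phase: nominal 42 - 21 = 21 days. Range 21 - 7 - 5 = 9 to 21 + 7 + 5 = 33 days.

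**Gain from asking at the call.** Gain = wait to next visit minus time to be seen after the call. I use 7 days, the longest that section 6.1 allows.

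| Phase | Nominal | Shortest | Longest |
|---|---|---|---|
| 4-week | 14 - 7 = 7 days | 2 - 7 < 0, so none | 26 - 7 = 19 days |
| 6-week | 21 - 7 = 14 days | 9 - 7 = 2 days | 33 - 7 = 26 days |

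The script's 2-3 days is not used as the time to be seen, because a call back from the study doctor would satisfy it.

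These figures apply only to a symptom that has begun before the call and that the patient does not volunteer.

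**The case against.** The strongest reply is that several other safeguards would have to fail together. Patients are trained to call at once; item 14 invites any other concern; and the closing text, used when nothing is positive, reminds the patient to phone the study team, or the kidney doctor on call after hours, if unwell. Every one of the 20 WATCH visits has an examination, a BVAS and laboratory data marked, and section 6 names creatinine and urinalysis among the routine results recorded at enrollment. Adverse events are sought at each contact and reviewed monthly (sections 8.2 and 8.3). The content of the symptom training is not shown, and the phone call template listed in Appendix D may hold these fields.

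This stands as a limit on consequence. It makes delay, not a missed relapse, the likely harm. It does not answer the omission: the other safeguards either depend on the patient recognizing and raising the symptom or act at visits, and the call exists as an additional check between them.

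A reader might infer from the 'If yes' branch that a symptom already handled by an outside doctor has no written route to a study evaluation. The documents do not support that. It is true of the appendix only; the one-week rule in section 6.1 applies whoever was called. The gap also does not arise if the study doctor was called, or if the patient's own nephrologist also does the study examinations.

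**Conclusion.** The point holds as a low-cost safety improvement. The script omits a direct renal and urinary question in a trial where renal relapse is a major event. Where the omission matters, asking would bring evaluation forward by nominally about 7 days in the 4-week phase (range none to 19) and about 14 days in the 6-week phase (range 2 to 26). This assumes that the symptom began before the call, was not volunteered, and would be evaluated 7 days after being reported.

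The documents do not say how many renal relapses cause symptoms that a patient could notice, so neither the number of relapses affected nor the size of the harm can be estimated. A reader might go further and infer that relapses are lost, or that time to first relapse or the stopping rule is distorted. Nothing in the documents establishes either, and neither is claimed here.

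The relay matter is secondary: the script should carry out a rule that already binds.

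**What to change.** In Appendix C:

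1. Add direct questions on red, dark or foamy urine; on reduced urine or urinary symptoms; and on leg or face swelling.
2. In the 'If yes' branch, also relay any symptom suggestive of relapse to the study doctor, so that the script carries out the visit within a week required by section 6.1.

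Cost: an assumed 0.5 to 2 minutes per call. Over at most 19 calls that is 19 x 0.5 = 9.5 to 19 x 2 = 38 minutes per patient. There would also be a few extra relays or clinic visits, and a script amendment with IRB review. If the phone call template already holds these questions, only the script text needs to be brought into line.

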## APPENDIX D: Case Report Forms

The following case report forms and logs will be used in this study:

1. Enrollment visit template CD5+
2. Enrollment Log CD5+
3. Phone call template CD5+
4. Randomization template CD5+
5. After randomization visit template CD5+
6. Concomitant Medications log CD5+
7. External reviewer relapse assessment template
8. Unexpected- Serious Adverse Event log CD5+
9. Delegation of responsibility log CD5+
10. Informed consent process documentation
11. Combined Damage Index CD5+
12. BVAS WG CD5+
13. Adverse Events Forms: AE and SAE
